### **Adverse events of special and possible interest**

Preferred terms used to identify adverse events of special interest (AESIs) and adverse events of possible interest (AEPIs) will be listed before database lock (DBL) and documented in the Study Master File. Grouped summary tables of certain MedDRA preferred terms will be produced and may also show the individual preferred terms which constitute each AESI/AEPI grouping. For each 'grouped' term, the number (%) of patients experiencing any of the specified terms will be presented by maximum CTCAE grade. Additional summaries will include Time to Onset of first CTCAE grade 3 or 4. Time to onset of first AE for each grouped term and preferred term within it will also be produced. Groupings will be based on preferred terms provided by the medical team prior to DBL, and a listing of the preferred terms in each grouping will be provided.

Additional summaries of the above-mentioned grouped AE categories will include number (%) of patients who have:

- At least one AESI/AEPI presented by outcome
- At least one AESI/AEPI causally related to study medication (as determined by the reporting investigator)
- At least one AESI/AEPI leading to discontinuation of IP

A summary of time to resolution to grade 1 or less and time to resolution to grade 2 or less will be provided.

Additionally, there will be several summaries of AESIs/AEPIs requiring concomitant treatment, and particularly the relationship of AESIs/AEPIs to the use of immunosuppressive agents (i.e., depicting which AESI/AEPI triggered immunosuppressive use) and, separately, to the use of immunosuppressive agents at high doses (High dose is defined as  $\geq 40$ mg of prednisone or equivalent per day).

### **Immune-mediated Adverse events (imAEs)**

The imAEs (as classified by the Sponsor) will be summarized in the similar manner as for the summaries for AESI/AEPI described above. The Sponsor will be responsible for producing these summaries.

### **Infection AEs**

These AEs will be summarized by pooled terms and PTs in two ways: (1) using MedDRA HLGT/HLT pooled terms (2) Custom pooled terms. The list of terms will be provided in a separate excel file. The following summaries will be reported for both HLGT/HLT pooled terms and custom pooled terms and PTs:

- Infection Adverse Events by pooled term and PT
- Causally-related Infection AEs by pooled term and PT
- Serious Infection AEs by pooled term and PT
- Causally-related Serious Infection AEs by pooled term and PT
- Infection AEs with maximum CTCAE grade by pooled term and PT
- Infection AEs with outcome of death by pooled term and PT
- Infection Adverse Events leading to treatment discontinuation by pooled term and PT
- Infection Adverse Events leading to dose delay or interruption by pooled term and preferred term
- Infection Adverse Events -List of preferred terms

#### **Haemorrhages-related adverse events**

Treatment-emergent haemorrhage events will be identified using the Haemorrhage (excluding laboratory terms) Standardized Medical Dictionary for Regulatory Activities (MedDRA) Query (SMQ) from the current MedDRA version.

The following key summary tables and listings will be produced for the subset of patients who are reported to have a treatment-emergent adverse event within the Hemorrhage SMQ:

- Haemorrhage SMQ patient disposition (all patients)
- Haemorrhage SMQ Demographic characteristics (Safety Analysis Set)
- Haemorrhage SMQ Disease characteristics at initial diagnosis or study entry (Safety Analysis Set)
- Haemorrhage SMQ Extent of disease at study entry (Safety Analysis Set)
- Haemorrhage SMQ Adverse events in any category - patient level (Safety analysis set)
- Haemorrhage SMQ Adverse events and event rate by system organ class and preferred term (Safety analysis set)
- Haemorrhage SMQ Time to onset of adverse event (days), arranged by system organ class and preferred term (Safety analysis set)
- Haemorrhage SMQ Causally related adverse events by system organ class and preferred term (Safety analysis set)
- Haemorrhage SMQ Adverse events by system organ class, preferred term, and maximum reported CTCAE grade (Safety analysis set)
- Haemorrhage SMQ Adverse events of CTCAE grade 3 or 4 by system organ class and preferred term (Safety analysis set)
- Haemorrhage SMQ Causally related adverse events of CTCAE grade 3 or 4 by system organ class and preferred term (Safety analysis set)
- Haemorrhage SMQ All deaths (Safety Analysis Set)

- Adverse events with outcome of death, by system organ class and preferred term (Safety analysis set)
- Haemorrhage SMQ Adverse events with outcome of death, causally related to study treatment, by system organ class and preferred term (Safety analysis set)
- Haemorrhage SMQ Serious adverse events by system organ class and preferred term (Safety analysis set)
- Haemorrhage SMQ Serious adverse events, causally related to study treatment, by system organ class and preferred term (Safety analysis set)
- Haemorrhage SMQ Adverse events, leading to discontinuation of study treatment, by system organ class and preferred term (Safety analysis set)
- Haemorrhage SMQ Listing of Deaths (Safety Analysis Set)
- Haemorrhage SMQ Serious adverse events - Listing of key information (Safety analysis set)
- Haemorrhage SMQ Impact of concomitant medication with potential risk of bleeding on the occurrence of the most severe bleed within each patient (Safety analysis set)
- Haemorrhage SMQ Medical history of bleeding (Safety analysis set)

#### **Summary of long-term tolerability:**

To assess long term tolerability, provided that there are a sufficient number of patients with events to warrant it, prevalence plots, life table plots and cumulative incidence plots will be presented for each of the AESI grouped terms and any other events considered important after review of the safety data, provided there are  $\geq 10$  events, that is 10 events in at least one treatment group.

A prevalence plot provides information on the extent to which the events may be an ongoing burden to patients. The prevalence at time  $t$  after first dose of study treatment is calculated as the number of patients experiencing the event divided by the number of patients receiving study treatment or in safety follow-up at time  $t$ ; generally,  $t$  is categorized by each day after dosing. The prevalence will be plotted over time presented. Multiple occurrences of the same event are considered for each patient but a patient is only counted in the numerator whilst they are experiencing one of the occurrences of the event. These plots will only be produced for AESIs that have  $\geq 10$  events, that is 10 events in at least one treatment group.

For each AESI, median time to first onset of the AESI from the date of first dose will be presented in patients in the safety analysis. Patients who did not experience the AESI will be censored at the end of their safety follow-up. Summary tables of time to first onset for each AE will also be produced (e.g. 1-28 days, 29-56 days, 57-84 days, 85-112 days, >112 days). Median duration of the AE and AESI will be presented in patients who experienced each, as well as the median time to resolution to grade 1 or less and time to resolution to grade 2 or less.

A life table plot can be used to describe the time to onset of the event and specifically when patients are at most risk of first experiencing the event. The hazard, or in other words, the probability of having an AE in a specified time period (e.g. 0-1 months, 1-3 months, 3-6

months, etc.) given that the patient reaches that time period without having an event is plotted for each time period. These plots will only be produced for AESIs that have  $\geq 10$  events, that is 10 events in at least one treatment group.

A cumulative incidence plot of the raw cumulative incidence over time will be presented. The raw cumulative incidence is the actual probability that a patient will have experienced their first occurrence of the event by a given time point. These plots will only be produced for AESIs that have  $\geq 10$  events, that is 10 events in at least one treatment group.

#### **4.2.13.2 Laboratory assessments**

Data obtained up until the 90 days following discontinuation of IP or until the initiation of the first subsequent therapy following discontinuation of IP (whichever occurs first) will be used for reporting. This will more accurately depict laboratory toxicities attributable to IP only as a number of toxicities up to 90 days following discontinuation of IP are likely to be attributable to subsequent therapy.

Data summaries and listings will be provided in International System (SI) of units.

All laboratory data will be listed. Flags will be applied to values falling outside - reference ranges (which will be explicitly noted on these listings where applicable), and to values for which CTCAE grading applies.

Scatter plots (shift plots) of baseline to maximum/minimum value (as appropriate) on treatment (i.e. on treatment is defined as data collected between the start of treatment and the relevant follow-up period following the last dose of IP) may be produced for certain parameters if warranted after data review.

Boxplots of absolute values by week, and boxplots of change from baseline by week, may be presented for certain parameters if warranted after data review up to Week 40.

Shift tables for laboratory values by worst common toxicity criteria (CTCAE) grade will be produced, and for specific parameters separate shift tables indicating hyper- and hypo-directionality of change will be produced. The laboratory parameters for which CTCAE grade shift outputs will be produced are:

- Hematology: Hemoglobin, Leukocytes, Lymphocytes, absolute count, Neutrophils, absolute count, Platelets
- Clinical chemistry: ALT, AST, Alkaline Phosphatase (ALP), Total bilirubin, Albumin, Magnesium – hypo and – hyper, Sodium – hypo and – hyper, Potassium – hypo and – hyper, Corrected calcium – hypo and – hyper, Glucose – hypo and – hyper, GGT, Creatinine

For the parameters with no CTCAE grading that are listed in the CSP, shift tables from baseline to worst value on treatment will be provided. Additional summaries will include a

shift table for urinalysis (Bilirubin, Blood, Glucose, Ketones, Protein) comparing baseline value to maximum on treatment value.

### Hy's law

The following summaries will include the number (%) of patients who have:

- Elevated ALT, AST, and Total bilirubin during the study

ALT

$\geq 3x - \leq 5x$  ULN Upper Limit of Normal (ULN) during the study

$> 5x - \leq 8x$  ULN

$> 8x - \leq 10x$  ULN

$> 10x - \leq 20$  ULN

and  $> 20x$  ULN

AST

$\geq 3x - \leq 5x$  ULN

$> 5x - \leq 8x$  ULN

$> 8x - \leq 10x$  ULN

$> 10 - \leq 20$  ULN

and  $> 20x$  ULN

Total bilirubin

$\geq 2x - \leq 3x$  ULN,

$> 3x - \leq 5x$  ULN,

$> 5x$  ULN during the study

ALT or AST

$\geq 3x - \leq 5x$  ULN,

$> 5x - \leq 8x$  ULN,

$>8x \leq 10x$  ULN,

$>10 \leq 20$  ULN

and  $>20x$  ULN during the study

- ALT or AST  $\geq 3x$  ULN and Total bilirubin  $\geq 2x$  ULN during the study (Potential Hy's law: The onset date of the ALT or AST elevation should be prior to or on the date of the Total bilirubin evaluation.)
- Narratives will be provided in the CSR for patients who have ALT  $\geq 3x$  ULN plus Total bilirubin  $\geq 2x$  ULN or AST  $\geq 3x$  ULN plus Total bilirubin  $\geq 2x$  ULN at any visit.

Liver biochemistry test results over time for patients with elevated ALT (i.e.  $\geq 3x$  ULN) or AST (i.e.  $\geq 3x$  ULN), and elevated total bilirubin (i.e.  $\geq 2x$  ULN) (at any time) will be plotted. Individual patient data where ALT or AST plus Total bilirubin are elevated at any time will be listed also.

Plots of ALT and AST vs. Total bilirubin will also be produced with reference lines at  $3 \times$ ULN for ALT, AST, and  $2 \times$ ULN for Total bilirubin. In each plot, Total bilirubin will be in the vertical axis.

### **Abnormal Thyroid function**

Elevated TSH will be summarized per treatment group in terms of number (%) of patients with elevated TSH (higher than the upper normal range), low TSH (lower than lower normal range), elevated TSH post-dose and within normal range at baseline, low TSH post-dose and within normal range at baseline.

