Table 2 Schedule of assessments for the MEDI4736 + tremelimumab combination or MEDI4736 monotherapy arms and optional retreatment period for MEDI4736 + tremelimumab combination arm

	Screening	C1 ^a	C2	C3	C4	C5	C6	C7	C8 until PD
Week	-4 to -1	0	4	8	12	16	20	24	28, 32, 36, 40, 44 (+4-wk intervals)
Day	-28 to -1	1	29	57	85	113	141	169	197, 225, 253, 281, 309 (+28-day intervals)
Window (days)*	NA	NA	±3	±3	±3	±3	±3	±3	±3
Informed consent	X ^b								
Study procedures									
Physical examination (full)	X								
Medical history, past and current	X								
Targeted physical examination (based on symptoms)		X	X	X	X	X	X	X	X
Vital signs ^c	X	X	X	X	X	X	X	X	X
ECG ^d	X	As clinically indicated							
Concomitant medications	<----- ----->								
Demography, including baseline characteristics and tobacco use	X								
HPV for oropharyngeal tumors only ^e	X ^b								
Eligibility criteria	X								
Pharmacokinetics^f									
MEDI4736 PK sample (serum)		X ^h	X ^g		X ^{g,h}			X ^g	
Tremelimumab PK sample (serum; combination therapy arm only)		X ^h	X ^g		X ^{g,h}				
Laboratory assessments									
Clinical chemistry	X	X ⁱ	X	X	X	X	X	X	X
Hematology	X	X ⁱ	X	X	X	X	X	X	X

	Screening	C1 ^a	C2	C3	C4	C5	C6	C7	C8 until PD
Week	-4 to -1	0	4	8	12	16	20	24	28, 32, 36, 40, 44 (+4-wk intervals)
Day	-28 to -1	1	29	57	85	113	141	169	197, 225, 253, 281, 309 (+28-day intervals)
Window (days)*	NA	NA	±3	±3	±3	±3	±3	±3	±3
TSH (and reflex free T ₃ or free T ₄) ^j	X	X ⁱ	X	X	X	X	X	X	X
Urinalysis	X	As clinically indicated							
Hepatitis B surface antigen, Hepatitis C antibody, and HIV	X								
Pregnancy test ^k	X	X	X	X	X	X	X	X	X
WHO/ECOG performance status	X	X	X	X	X	X	X	X	X
AE/SAE assessment	<----->								
Drug accountability		X	X	X	X	X	X	X	X
IP administration									
Monotherapy arm									
MEDI4736 ^l		X	X	X	X	X	X	X	X
Combination therapy arm									
MEDI4736 (combination therapy) ^{l,m}		X	X	X	X	X	X	X	X
Tremelimumab ^{l,m}		X	X	X	X				
Patient-reported outcome assessments^{n,f}									
EORTC QLQ-C30, CCI [REDACTED]	X	X	q8w (±3 days) relative to the date of Cycle 1 Day 1						
EORTC QLQ-H&N35, CCI [REDACTED]	X	X	q4w (±3 days) relative to the date of Cycle 1 Day 1						
Other laboratory assessments and assays									
Immunogenicity assessment (ADA sampling [including ADA neutralizing antibodies] to identify ADA responses in patient circulation) for MEDI4736 and tremelimumab ^f		X			X			X	

	Screening	C1 ^a	C2	C3	C4	C5	C6	C7	C8 until PD

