Patient-reported outcome assessments^o									
EORTC QLQ-C30, CCI	X	X						q8w (±3 days) relative to the date of Cycle 1 Day 1	
EORTC QLQ-H&N35, CCI	X	X						q4w (±3 days) relative to the date of Cycle 1 Day 1	
Other laboratory assessments and assays									
Tumor biopsy or obtain archival tumor tissue <3 years old for PD-L1 status	X ^c								
Tumor evaluation (CT or MRI) (RECIST 1.1) ^q	X	First on-treatment scan at 6 weeks (+1 week) and then q6w (±1 week) for the first 24 weeks relative to the date of randomization and then q8w (±1 week) thereafter							

CCI

Window for visits is relative to day of dosing, even if dosing is delayed, unless otherwise specified.

- ^a Cycle 1 Day 1 procedures do not need to be repeated if the same procedures were performed for screening purposes 3 days prior to Cycle 1 Day 1.
- ^b Patient visits will change from q3w to q4w after completion of chemotherapy.
- ^c Informed consent of study procedures and tumor sample acquisition may be obtained prior to the 28-day screening window, if necessary, in order to permit tumor sample acquisition and analysis prior to randomization. PD-L1 testing will be done from a newly acquired tumor biopsy (preferred) or archival tissue (<3 years old).
- ^d Pre-dose and as clinically indicated before every infusion or administration.
- ^e Any clinically significant abnormality detected requires a confirmatory ECG.
- ^f HPV status testing may be performed for oropharyngeal tumors only. Local testing is acceptable and preferred. If HPV status is unknown or unavailable locally, a newly acquired or archived tumor sample must be submitted for central testing at a reference laboratory as described in the Laboratory Manual.
- ^g To be collected q3w prior to the start of infusion and as clinically indicated. Electrolytes should be monitored with cetuximab therapy as per institution guidelines.

- h If screening assessments are performed within 3 days prior to Day 1 (first infusion day), they do not need to be repeated at Day 1.
- i If the patient does not complete treatment through Cycle 5, TSH should be obtained after the patient's last cycle.
- j Free T₃ or free T₄ will only be measured if TSH is abnormal or if there is clinical suspicion of an AE related to the endocrine system.
- k For women of childbearing potential only. A pregnancy test must be performed within 7 days before Cycle 1 Day 1. A urine or serum pregnancy test is acceptable.

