5.2 Safety assessments

5.2.1 Laboratory safety assessments

Blood and urine samples for determination of clinical chemistry, hematology, and urinalysis will be taken at the times indicated in the assessment schedules (see [Table 2](#), [Table 3](#), and [Table 4](#)).

Clinical laboratory safety tests will be performed in a licensed clinical laboratory according to local standard procedures. Hematology, clinical chemistry, and urinalysis tests will be performed by the hospital's local laboratory. Urine pregnancy tests may be performed at the site using a licensed test. Sample tubes and sample sizes may vary depending on the laboratory method used and routine practice at the site. Clinically significant abnormal laboratory results should be repeated as soon as possible (preferably within 24 to 48 hours).

Additional safety samples may be collected if clinically indicated at the discretion of the Investigator. The date, time of collection, and results (values, units, and reference ranges) will be recorded on the appropriate eCRF.

The laboratory variables to be measured are presented in [Table 5](#) (clinical chemistry), [Table 6](#) (hematology), and [Table 7](#) (urinalysis).

Note: For coagulation parameters, activated partial thromboplastin time and international normalized ratio are to be assessed at baseline and as clinically indicated.

Pregnancy tests on either urine (human chorionic gonadotropin [hCG]) or blood (serum β -hCG) samples will be performed for pre-menopausal women of childbearing potential at Screening and subsequent visits as specified in the assessment schedule (see [Table 2](#), [Table 3](#), and [Table 4](#)). Tests will be performed by the hospital's local laboratory unless otherwise specified. If results are positive, the patient must not start or continue treatment. In the event of a suspected pregnancy during the study, the test should be repeated.

Other safety tests to be performed at screening include assessment for hepatitis B surface antigen, hepatitis C antibodies, HIV antibodies, and thyroid-stimulating hormone (TSH). Free triiodothyronine or free thyroxine will also be measured if the results of the TSH are abnormal or if there is clinical suspicion of an AE related to the endocrine system.

Table 5 Clinical chemistry (serum or plasma)

Albumin	Glucose
Alkaline phosphatase ^a	Lactate dehydrogenase
ALT ^a	Lipase
Amylase	Magnesium ^{b,c}
AST ^a	Potassium
Bicarbonate ^b	Sodium
Calcium	Total bilirubin ^a

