**Table 3 Safety Objectives**

Safety Objective:	Outcome Measures:
To assess the safety and tolerability profile of MEDI4736 + tremelimumab combination therapy and MEDI4736 monotherapy compared to SoC (EXTREME) in the first-line setting for treatment of SCCHN	AEs, physical examinations, laboratory findings (including clinical chemistry, hematology, and urinalysis), vital signs (including blood pressure and pulse), and ECGs in the PD-L1 TC/IC high subgroup, low risk of EM subgroup and all-comers

AE Adverse Event; ECG Electrocardiogram; EM Early mortality; SoC Standard of Care; IC Tumor-associated immune cells; TC Tumor cells

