### 3.3.4 Laboratory data

Laboratory data will be collected throughout the study, from screening to the follow-up visits as described in Tables 2, 3 and 4 of the CSP. Blood and urine samples for determination of hematology, clinical chemistry, and urinalysis will be collected as described in Section 5.2.1

of the CSP. For derivation of baseline and post baseline visit values considering visit window and how to handle multiple records, derivation rules as described in Section 3.3.7 below will be used.

Change from baseline in hematology and clinical chemistry variables will be calculated for each post-dose visit on treatment. CTCAE grades will be defined at each visit according to the CTCAE grade criteria using local or project ranges as required, after conversion of lab result to corresponding SI units. The following parameters have CTCAE grades defined for both high and low values: Potassium, Sodium, Magnesium, Glucose and Corrected calcium so high and low CTCAE grades will be calculated.

Corrected Calcium will be derived during creation of the reporting database using the following formula:

$$\text{Corrected calcium (mmol/L)} = \text{Total calcium (mmol/L)} + ([40 - \text{Albumin (G/L)}] \times 0.02)$$

Absolute values will be compared to the project reference range and classified as low (below range), normal (within range or on limits of range) and high (above range).

The maximum or minimum on treatment value (depending on the direction of an adverse effect) will be defined for each laboratory parameter as the maximum (or minimum) post-dose value at any time.

Local reference ranges will be used for the primary interpretation of laboratory data. The denominator used in laboratory summaries of CTCAE grades will only include evaluable patients, in other words those who had sufficient data to have the possibility of an abnormality.

For example:

- If a CTCAE criterion involves a change from baseline, evaluable patients would have both a pre-dose and at least 1 post-dose value recorded.
- If a CTCAE criterion does not consider changes from baseline, to be evaluable the patient needs only to have 1 post dose-value recorded.

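### Scheduled TSH testing is denser in the immunotherapy arms than in SoC, and the by-arm count of patients with any abnormal TSH makes no allowance for it, so the descriptive thyroid contrast may be inflated

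*SAP*

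**What the plan says.** **Objective.** SAP Table 3 (Safety Objectives) words the safety aim as a contrast, ending in "MEDI4736 monotherapy compared to SoC (EXTREME) in the first-line setting for treatment of SCCHN". Laboratory findings are among its outcome measures.

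**Immunotherapy schedule.** In Protocol Table 2 the row "TSH (and reflex free T" is marked at screening, Cycle 1 and every later cycle. The last column runs "28, 32, 36, 40, 44 (+4-wk intervals" until progression.

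**SoC schedule.** In Protocol Table 3 the same row is marked only at screening, Cycle 5 (week 12, day 85) and week 24. Footnote i covers early stoppers: "If the patient does not complete treatment through Cycle 5, TSH should be obtained after the patient's last cycle".

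**After treatment.** Protocol Table 4 gives every arm one TSH at Day 30 after the last dose and none at months 2 or 3. Protocol 5.2.1 allows extra tests: "Additional safety samples may be collected if clinically indicated at the discretion of the Investigator".

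**Analysis.** The thyroid paragraph of SAP 4.2.13.2 begins "Elevated TSH will be summarized per treatment group in terms of number (%) of patients with elevated TSH". It goes on to count patients with low TSH, and with high or low post-dose TSH after a normal baseline. SAP 3.3.4 says the laboratory extreme "will be defined for each laboratory parameter as the maximum (or minimum) post-dose value at any time". SAP 3.3.7 lets unscheduled values count towards extremes and treats Day 1 laboratory values as pre-dose. SAP 4.2.13.2 uses data to 90 days after treatment or to the first subsequent therapy, whichever comes first. Neither document limits the TSH counts to common time points or relates them to the number of tests.

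**The concern.** The proportion of patients with at least one abnormal value rises with the number of times each patient is tested. Here the number of scheduled tests is set by the arm. Some excess of abnormal TSH on immunotherapy could therefore come from the calendar rather than the drug, and the table gives no means of separating the two.

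This matters because hyper- and hypothyroidism belong to a named adverse event of special interest, and percentages placed side by side will be read as a treatment difference. Protocol 6.3.4 also limits adverse event reporting of deterioration in mandated laboratory values to cases that are serious or lead to discontinuation, with symptoms reported in their own right. Asymptomatic TSH abnormality may therefore show mainly in these laboratory outputs. The protocol recognises the general problem for imaging: Appendix E asks sites to keep to the scan schedule so that unequal assessment frequency does not bias results.

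**Working it through.** The plan gives no TSH rate or power figure, so there is none to reproduce. The check counts tests and then asks what the schedules alone would produce.

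**Step 1: scheduled post-dose tests** (Protocol Tables 2, 3 and 4; Cycle 1 Day 1 is excluded as pre-dose).

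| Time on treatment | Immunotherapy, on treatment | SoC, on treatment | With Day 30 |
|---|---|---|---|
| 12 weeks | 3 | 1 | 4 vs 2 |
| 24 weeks | 6 | 2 | 7 vs 3 |
| 48 weeks | 12 | 2 | 13 vs 3 |

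**Step 2: independent tests, no drug effect.** Assume the same chance p of a high result per test in each arm. Neither document gives p; 2.5% is used, with a range of 1% to 5%. The chance of at least one high value in k tests is 1 − (1 − p)^k. Day 30 is included.

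- 12 weeks, p = 2.5%: 1 − 0.975^4 = 9.6% vs 1 − 0.975^2 = 4.9%.
- 24 weeks, p = 2.5%: 1 − 0.975^7 = 16.2% vs 1 − 0.975^3 = 7.3%.
- 24 weeks, p = 1%: 6.8% vs 3.0%; p = 5%: 30.2% vs 14.3%.
- 48 weeks, p = 2.5%: 1 − 0.975^13 = 28.0% vs 7.3%.

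**Step 3: correlated tests.** Repeat TSH values in one patient are unlikely to be independent. Each value was simulated as √ρ·b + √(1 − ρ)·e, where b is a patient-level and e a test-level standard normal. A value above the 97.5th percentile counts as high, so p stays at 2.5% (400,000 patients).

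| ρ | 24 weeks (7 vs 3 tests) | Ratio | 48 weeks (13 vs 3 tests) |
|---|---|---|---|
| 0 | 16.2% vs 7.3% | 2.2 | 28.0% vs 7.3% |
| 0.5 | 11.4% vs 6.3% | 1.8 | 16.8% vs 6.3% |
| 0.8 | 7.4% vs 4.9% | 1.5 | 9.7% vs 4.9% |

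**Step 4: real but transient episodes.** Take one episode with onset uniform over 24 weeks on treatment. The 4-weekly schedule catches essentially all episodes of 4 weeks or more. Testing at weeks 12 and 24 catches about 33%, 50% and 67% of episodes lasting 4, 6 and 8 weeks. At 12 weeks or longer, both schedules catch them.

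**Step 5: shared time points only.** Restricting both arms to week 12, week 24 and Day 30 gives 3 vs 3 tests. With p = 2.5% and independence, the expected share is 7.3% in each arm.

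**The case against.** The strongest reply is that little hangs on this table. SAP 4.2.13 plans no formal analysis of safety data, so no difference, interval or test is attached to it. Thyroid events have separate outputs: grouped special-interest tables by grade, time to onset, cumulative incidence where numbers allow, event rates per 100 patient-years, and immune-mediated events identified partly through endocrine therapy. All laboratory data are listed, so test dates can be seen. Showing more risk for the experimental drug is also the cautious direction.

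Most of that stands, and it limits the weight of the point. It does not remove the imbalance from a by-arm table that serves an objective framed against SoC.

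Three stronger readings are tempting, and the documents do not support them:

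- A reader might infer that SoC patients are tested only at weeks 12 and 24. Table 4 adds Day 30, footnote i moves the week-12 test for early stoppers, and unscheduled tests are allowed in any arm. Unscheduled SoC tests could narrow the gap.
- A reader might infer a fixed two-fold excess. That needs roughly independent tests; correlation lowers it. The 24-week comparison also describes only patients treated that long. Protocol 1.1.6 expects progression within 6 months on EXTREME, so many SoC patients will stop near or before week 24, and the Day-30 test drops out if subsequent therapy starts first.
- A reader might infer that the table is bound to show an excess without a drug effect, or that any excess is artefact. A real thyroid effect is plausible, and abnormalities of 12 weeks or more that begin in the first 24 weeks are found on either schedule.

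**Conclusion.** The point holds as a limit on how one descriptive table can be read. The schedules give 7 vs 3 scheduled post-dose tests for patients treated to week 24, and the gap widens afterwards. The any-time count takes no account of this, so the contrast with SoC may be inflated by schedule alone. That the count is any-time is a reading of SAP 3.3.4 and 3.3.7; the thyroid paragraph does not use the words.

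The direction follows from the schedules. The size does not: the range of about 1.5- to 2.2-fold at 24 weeks rests on an assumed 2.5% per-test rate, equal in both arms, and on within-patient correlation between 0 and 0.8. No efficacy result or error rate is affected.

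**What to change.** In SAP 4.2.13.2, add a by-arm TSH table restricted to the time points scheduled in every arm: baseline, week 12 (immunotherapy Cycle 4, SoC Cycle 5), week 24, and Day 30 after the last dose. Use the patients tested at each time point as the denominator. Assign SoC early-stopper tests by the visit-window rules of SAP 3.3.7, with the same day limits in all arms. Use this table for the between-arm reading.

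Keep the any-time table as a within-arm description, because it is the one that captures transient events. Add the number of TSH tests per patient by arm, and a note that the arms are not directly comparable on it.

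The cost is one table and one added row from data already collected; no sample or schedule changes. The matched table uses fewer immunotherapy results and will miss some short episodes. Its week-24 row covers only patients still being tested, a selection made after randomization. SAP 3.3.7 suppresses visits with few observations, so the amendment should state whether that rule applies to this row.
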